#### **8.3.1.2 Time to PASI75, PASI90 and PASI100 response**

Time to PASI75, PASI90, and PASI100 response (in days) will each be calculated as:

$$\text{Min}(\text{Date of first PASI}_{xx} \text{ response}) - \text{Date of Baseline visit} + 1,$$

where xx represents 75, 90, 100 respectively. All visits including unscheduled visits are considered.

Subjects who discontinue study treatment without achieving a given PASI response prior to discontinuation will be censored at the date of the last observed PASI assessment on or prior to the date of treatment discontinuation. Subjects who reach the Week 48 Visit without achieving the given response will be censored at the date of the last observed PASI assessment on or prior to the Week 48 Visit. Subjects will be censored at Baseline if there is no Baseline PASI assessment or no Post Baseline PASI assessment

Time to PASI75, PASI90, and PASI100 response during the initial and maintenance treatment period will each be estimated and presented using the Kaplan-Meier product-limit method based on the RS by initially randomized treatment groups (bimekizumab vs secukinumab).

Time to a given response will be defined as the length in days from the first dose of IMP until the first date when the response is achieved. The median time to response, including the two-sided 95% CI, will be calculated for each treatment. Between group differences (bimekizumab vs secukinumab) will be analyzed with the log-rank statistic by region and prior biologic exposure. Kaplan-Meier plots of time to PASI responses will also be presented by initially randomized treatment group. In these Kaplan-Meier plots, the line will start at 0 (since there are no responders at Week 0) and will increase over time, representing time to achieving the response.

Time to PASI75, PASI90, and PASI100 response analyses will not be conducted for the OLE and the OLE2 treatment periods.

### 8.3.1.3 PASI score

Absolute and percent change from Baseline in PASI score is defined in Section 8.1.1.1.

The percentage of subjects with absolute PASI score  $\leq 1$ ,  $\leq 2$ ,  $\leq 3$  and  $\leq 5$  will be presented over time using NRI for the RS, the MS, and the OLS.

Absolute PASI score categories will not be summarized for the OLE2 treatment period.

### 8.3.2 IGA response

- IGA response (Clear) is defined when IGA score is clear [0] (Table 8–1) with at least a two-category improvement from Baseline at visit time point.
- IGA response (Clear or Almost Clear with at least 2 category improvements relative to Baseline) is defined as IGA score of clear [0] or almost clear [1] with at least a two-category improvement from Baseline at visit time point.
- Shift from Baseline in IGA score is defined at each Post-Baseline visit time point relative to Baseline.
- Scalp-specific IGA response

A static IGA for scalp PSO will be used to assess disease severity on the scalp.

All subjects will complete the scalp IGA at Baseline. Only subjects with scalp involvement at Baseline will complete the scalp IGA at the other visits specified in the protocol. Subjects with scalp involvement at Baseline are defined as those with a scalp IGA score  $> 0$  at Baseline.

Scalp lesions will be assessed in terms of clinical signs of redness, thickness, and scaliness using a 5-point scale as outlined in Table 8–2 below.

**Table 8–2: Scalp IGA**

Score	Short Descriptor	Detailed Descriptor
0	Clear	Scalp has no signs of PSO; post-inflammatory hyperpigmentation may be present
1	Almost clear	Scalp has no thickening; normal to pink coloration; no to minimal focal scaling
2	Mild	Scalp has just detectable to mild thickening; pink to light red coloration; predominately fine scaling
3	Moderate	Scalp has clearly distinguishable to moderate thickening; dull to bright red, moderate scaling
4	Severe	Scalp has severe thickening with hard edges; bright to deep dark red coloration; severe/coarse scaling covering almost all or all lesions

Scalp IGA response is defined as clear [0] or almost clear [1] with at least a two-category improvement from Baseline. For analysis purposes, the evaluation of scalp IGA will be limited

to subjects with a Baseline scalp IGA of at least 2. Therefore, if a subject has a score of 2 at Baseline, they can only be considered a responder if their IGA is 0 (thereby meeting the criterion for a two-category improvement from Baseline). Subjects with a Baseline scalp IGA of 1 will be assessed per the protocol but will not be part of the scalp IGA analysis.

- pp-IGA response

A static IGA for palmoplantar PSO will be used to assess palmoplantar disease severity.

Only subjects with palmoplantar involvement at Baseline will complete the pp-IGA at the other visits specified in the protocol. Subjects with palmoplantar involvement at Baseline are defined as those with a pp-IGA score >0 at Baseline.

Palmoplantar disease will be assessed in terms of clinical signs of redness, thickness, and scaliness using a 5-point scale as outlined in [Table 8-3](#) below.

**Table 8-3: Palmoplantar IGA**

Score	Short Descriptor	Detailed Descriptor
0	Clear	Palmoplantar has no signs of PSO; post-inflammatory hyperpigmentation may be present
1	Almost clear	Palmoplantar has no thickening; normal to pink coloration; no to minimal focal scaling
2	Mild	Palmoplantar has just detectable to mild thickening; pink to light red coloration; predominately fine scaling
3	Moderate	Palmoplantar has clearly distinguishable to moderate thickening; dull to bright red and clearly distinguishable coloration; moderate scaling
4	Severe	Palmoplantar has severe thickening with hard edges; bright to deep dark red coloration; severe/coarse scaling covering almost all or all lesions; numerous fissures

PSO=psoriasis.

Palmoplantar IGA response is defined as clear [0] or almost clear [1] with at least a two-category improvement from Baseline. For analysis purposes, the evaluation of pp-IGA will be limited to subjects with a Baseline pp-IGA of at least 2. Therefore, if a subject has a score of 2 at Baseline, they can only be considered a responder if their IGA is 0 (thereby meeting the criterion for a two-category improvement from Baseline). Subjects with a Baseline pp-IGA of 1 will be assessed per the protocol but will not be part of the palmoplantar IGA analysis.

IGA response rate, Scalp IGA response rate, and Palmoplantar IGA response rate will be summarized for RS by treatment group and for OLS by treatment sequence and visit.

A line plot of the IGA responder rates (both clear or almost clear and clear) over time, by treatment group will be produced for the RS and by randomized treatment groups. This plot will include assessments from the Initial and Maintenance Treatment Period. An additional plot will be produced by re-randomized maintenance treatment groups only for the Maintenance Treatment Period for the MS. Additional plots will be produced based on the OLS and the OLS2 for IGA clear [0] and for IGA (clear [0] or almost clear [1]) only by treatment sequence.

### 8.3.3 Body Surface Area (BSA)

- Absolute change from Baseline in the BSA affected by PSO is defined as Post Baseline BSA minus Baseline BSA affected by PSO.
- Percent change from Baseline in BSA affected by PSO is defined as

$$\text{Percent change from Baseline} = 100 \times \frac{\text{Post Baseline BSA} - \text{Baseline BSA}}{\text{Baseline BSA}}$$

The percent of subjects with absolute BSA=0%, ≤1%, ≤3% and ≤5% will be presented over time using NRI.

BSA results will be listed but will not be summarized for the OLE2 treatment period.

### 8.3.4 Product of IGA and BSA (IGAxBSA)

- Absolute change from Baseline in the product IGAxBSA is defined as Post Baseline IGAxBSA minus product of Baseline IGAxBSA.
- Percent change from Baseline in the product of IGAxBSA is defined as

$$\text{Percent change from Baseline} = 100 \times \frac{\text{Post Baseline IGAxBSA} - \text{Baseline IGAxBSA}}{\text{Baseline IGAxBSA}}$$

The absolute and percentage change from baseline will be summarized for each study period (Initial randomized, Maintenance) by treatment group and visit.

The product of IGA and BSA will not be summarized for the OLE2 treatment period.

### 8.3.5 Dermatology Life Quality Index (DLQI)

The DLQI questionnaire is used for subjects with psoriasis and consists of 10-questions. This is a validated quality-of-life questionnaire that covers 6 domains including symptoms and feelings, daily activities, leisure, work and school, personal relationships, and treatment, as assessed over the past week.

The scoring of each answer for the DLQI is as follows:

**Table 8–4: Dermatology Life Quality Index**

DLQI Scoring	
Response	Score
Very much	3
A lot	2
A little	1
Not at all	0
Not relevant	0
Question unanswered	0
Q7: ‘prevented work or studying’ = yes	3

The DLQI total score is calculated by adding the score of each question. The maximum score is 30, and the minimum score is 0. The higher the score, the more quality of life is impaired.

**Meaning of DLQI Scores**

0-1 = no effect at all on patient’s life

2-5 = small effect on patient’s life

6-10 = moderate effect on patient’s life

11-20 = very large effect on patient’s life

21-30 = extremely large effect on patient’s life

This categorization will not be utilized in the analysis.

Because Q7 has a sub-question (referred to as Q7a here) after the leading yes/no question, some clarifying rules for scoring are provided:

- If Q7 is marked as “yes”, a score of 3 is given regardless of the responses to Q7a.
- If Q7 is marked as “no”, “not relevant”, or is missing and Q7a is “A lot”, a score of 2 is given.
- If Q7 is marked as “no”, “not relevant”, or is missing and Q7a is “A little”, a score of 1 is given.
- If Q7 is marked as “no”, “not relevant”, or is missing and Q7a is “Not at all”, a score of 0 is given.
- If Q7 is marked as “no” or “not relevant” and Q7a is missing, a score of 0 is given.
- If Q7 is missing and Q7a is missing, Q7 is considered unanswered (see below for details on how this impacts the overall DLQI score).

If 1 question is left unanswered, this is scored 0 and the scores are summed and expressed as usual out of a maximum of 30. If 2 or more questions are left unanswered, the questionnaire is not scored.

A subject is considered to have achieved the minimally clinically important difference (MCID) if their individual improvement from Baseline score is  $> 4$ . A 4-point improvement in the DLQI total score (DLQI response) has been reported to be meaningful for the subject (within-subject MCID).

The DLQI related efficacy variables are defined as follows:

- Change from Baseline in DLQI total score is defined as Post-Baseline DLQI total score minus Baseline DLQI total score.
- Percent of subjects achieving a DLQI total score of 0 or 1 is defined as the number of subjects with DLQI absolute score of 0 or 1 divided by the number of subjects in RS.
- Percent of subjects achieving a MCID in DLQI is defined as the number of subjects with improvement from Baseline total score of 4 or more divided by the number of subjects in RS. Only subjects with a Baseline DLQI total score of 4 or greater will be considered for this analysis.

The DLQI related efficacy variables will be summarized for the double-blind treatment visits separately for the RS and MS, and separately for OLS and OLS2 [DLQI(0/1) only] by treatment sequence respectively and visit.

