#### **2.2.1.3 Other efficacy variables**

The other efficacy variables are:

- PASI75, PASI90, and PASI100 response
- Time to PASI75, PASI90, and PASI100 response
- Absolute and percent change from Baseline in PASI
- Percentage of subjects with PASI  $\leq 1$ ,  $\leq 2$ ,  $\leq 3$ , and  $\leq 5$
- IGA response (Clear with at least 2 category improvement relative to Baseline)
- IGA response (Clear or Almost Clear with at least 2 category improvement relative to Baseline)
- Shift from Baseline in IGA score
- Absolute and percent change from Baseline in the body surface area (BSA) affected by PSO
- Percent of subjects with absolute BSA=0%,  $\leq 1\%$ ,  $\leq 3\%$  and  $\leq 5\%$
- Absolute and percent change from Baseline in the product of IGA and BSA (IGAxBSA)
- Change from Baseline in Dermatology Life Quality Index (DLQI) total score
- Percent of subjects achieving a DLQI total score of 0 or 1
- Percent of subjects achieving a minimal clinically important difference (MCID) (improvement from Baseline of 4 or more) in the DLQI total score

- Change from Baseline in the Patient's Global Assessment of Disease Activity (PGADA) for the arthritis visual analog scale (VAS) in subjects with psoriatic arthritis (PsA) at Baseline
- Shift from Baseline in Patient Global Assessment of PSO score
- Change from Baseline in symptoms of PSO (itch, pain, and scaling)
- Patient Symptom Diary responses for itch, pain, and scaling
- Change from Baseline in Modified Nail Psoriasis Severity Index (mNAPSI) score for subjects with nail PSO at Baseline
- mNAPSI75 response (defined as a subject that achieves at least a 75% reduction from Baseline in the mNAPSI score) for subjects with nail PSO at Baseline
- mNAPSI90 response (defined as a subject that achieves at least a 90% reduction from Baseline in the mNAPSI score) for subjects with nail PSO at Baseline
- mNAPSI100 response (defined as a subject that achieves a 100% reduction from Baseline in the mNAPSI score) for subjects with nail PSO at Baseline
- Scalp IGA response (clear or almost clear with at least a two-category improvement from Baseline) for subjects with scalp PSO at Baseline
- Palmoplantar Investigator's Global Assessment (pp-IGA) response (clear or almost clear with at least a two-category improvement from Baseline) for subjects with palmoplantar PSO at Baseline
- Responses to the European Quality-of-Life 5-Dimensions 3-Level (EQ-5D-3L) dimensions, absolute and changes from Baseline in EQ-5D-3L VAS scores

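### SAP Section 8.3.5 sets the DLQI MCID at an improvement greater than 4 in one sentence and at 4 or more everywhere else; the strict form is wrong as written

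*SAP*

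**What the plan says.** Section 8.3.5 of the SAP deals with the MCID in three places.

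- The subject-level rule: "A subject is considered to have achieved the minimally clinically important difference (MCID) if their individual improvement from Baseline score is" greater than 4.
- The rationale that follows directly: "A 4-point improvement in the DLQI total score (DLQI response) has been reported to be meaningful for the subject (within-subject MCID").
- The definition of the reported percentage: "the number of subjects with improvement from Baseline total score of 4 or more divided by the number of subjects in RS". The next sentence adds: "Only subjects with a Baseline DLQI total score of 4 or greater will be considered for this analysis".

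The endpoint list in Section 2.2.1.3 has: "Percent of subjects achieving a minimal clinically important difference (MCID) (improvement from Baseline of 4 or more) in the DLQI total score". Table 12–3 in Appendix D also labels the MCID row with a threshold of at least 4, and marks it for the Week 48, Week 96 and Week 144/OLE reporting.

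On the scale, the text around Table 8–4 says: "The maximum score is 30, and the minimum score is 0". Table 4–2 restricts DLQI to integer values.

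Section 8.3.5 has the DLQI variables summarized separately on the RS, the Maintenance Set (MS) and the Open-Label Set (OLS), with only DLQI 0/1 on Open-Label Set 2 (OLS2). Both DLQI percentages, 0/1 and MCID, are nevertheless written with the RS as denominator.

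**The concern.** A responder threshold should appear once, or identically wherever it appears. Here the sentence phrased as the classification rule for an individual subject excludes an improvement of exactly 4, while the sentence defining the reported percentage includes it. The SAP does not say which prevails. A programmer who codes the responder flag from the first sentence and a reader who interprets the table from Section 2.2.1.3 would be using different endpoints.

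What is at stake is the published proportion of subjects with a meaningful DLQI improvement, which recurs at several data cuts. The RS denominator is a smaller matter in the same lines: it is written for one analysis set although the summaries run on several.

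**Working it through.** The SAP gives no rate, sample size or power for this variable, so there is no figure to reproduce. The check is a comparison of the statements plus one logical test.

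**1. Scale.** Each question scores 0 to 3 (Table 8–4) and the total is the sum, from 0 to 30. Table 4–2 confirms integer values. On integers, improvement > 4 is the same as improvement ≥ 5.

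**2. Difference between the rules.** Let N be the number of subjects in the analysis and n₄ the number improving by exactly 4.

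- Rate under ≥ 4: (n₄ + n≥5) / N
- Rate under > 4: n≥5 / N
- Difference: n₄ / N

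Missing values are set to non-response (Section 4.2.1.3) under either rule, so they do not change the numerator of the difference.

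**3. Test at the eligibility boundary.** A subject with Baseline DLQI 4 is eligible. The lowest possible score is 0, so the largest possible improvement is 4 − 0 = 4.

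- 4 ≥ 4 is true: this subject can respond.
- 4 > 4 is false: this subject can never respond.

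An eligibility cut-off of 4 therefore matches the inclusive rule and not the strict one.

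**4. Statements side by side.**

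| Place | Threshold |
|---|---|
| 8.3.5, subject-level rule | > 4 |
| 8.3.5, rationale | a 4-point improvement is meaningful |
| 8.3.5, variable definition | ≥ 4 |
| 8.3.5, eligibility | Baseline ≥ 4, consistent only with ≥ 4 |
| 2.2.1.3, endpoint list | ≥ 4 |
| Table 12–3 | ≥ 4 |

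**5. Illustration only.** None of these inputs is in the SAP. Assume that 85% of eligible subjects improve by at least 4 and that 2%, 5% or 8% improve by exactly 4. The inclusive rule gives 85.0%. The strict rule gives 85 − 2 = 83.0%, 85 − 5 = 80.0% or 85 − 8 = 77.0%. This shows the mechanism and is not an estimate for this trial.

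**6. Denominator.** The RS is all randomized subjects (Section 3.5.2). The MS and OLS are defined by dosing at or after Week 16 and Week 48 (Sections 3.5.5 and 3.5.6). A percentage tabulated on the MS or OLS needs its own set as denominator, so a formula naming only the RS does not describe those tables.

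**The case against.** The best defence is that the intended rule is not in real doubt. Every other statement points to 4 or more, the formal definition is the bulleted one, and the strict inequality looks like a slip of one symbol. That stands as to intent. It does not make the sentence right, and the SAP contains no order of precedence. The symbol might also have been lost in reading the PDF. This is unlikely, since the at-least sign survives elsewhere, including in the next section, but the page should be checked. If it shows the at-least sign, the threshold part falls away.

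Three stronger readings should be resisted.

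- A reader might infer that subjects with Baseline DLQI below 4 stay in the denominator as failures. The sentence directly after the RS formula removes them from the analysis, so the natural joint reading is RS subjects with Baseline DLQI of at least 4. The SAP limits the PSD, scalp IGA and palmoplantar IGA responders by Baseline in a similar way. Deflated rates such as 0.85 × 0.90 = 76.5% need both an assumed eligible share and disregard of that sentence.
- A reader might infer that OLS2 responders would be divided by the RS. Section 3.6 confines OLE2 summaries to OLS2. Section 8.3 fixes observed case for DLQI 0/1 there, and Section 4.2.1.5 defines that as subjects with available data who have not discontinued. The MCID is not summarized on OLS2 at all.
- A reader might infer a threat to the trial's conclusions. The MCID response is outside H1 to H6 (Section 4.5) and absent from the nominal p-value list in Section 8.4, where the only DLQI entry is the 0/1 response.

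**Conclusion.** The threshold inconsistency is real: the strict inequality in Section 8.3.5 conflicts with the definition in the same section, with Section 2.2.1.3, with Table 12–3 and with the SAP's own eligibility rule. Its effect equals the proportion of analysed subjects who improve by exactly 4 points, which cannot be obtained from the document. It touches one descriptive rate for an other efficacy variable and no test. The denominator wording is a clarification to make alongside, because one formula naming the RS is used for summaries on several sets; it is not a second contradiction of the same weight. The threshold conclusion assumes that the inequality sign in the text at hand matches the SAP page.

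**What to change.** In Section 8.3.5, change the subject-level rule from greater than 4 to at least 4, so that it agrees with the variable definition, Section 2.2.1.3 and Table 12–3.

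In the same edit, replace the RS denominator in both DLQI percentages with the number of subjects in the analysis set being summarized. For the MCID, add that these are the subjects of that set with Baseline DLQI of at least 4. OLS2 needs no new rule; a cross-reference to the observed-case rule in Sections 4.2.1.5 and 8.3 is enough.

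The cost is a few words in the SAP and a check that the programmed responder flag uses at least 4. No data collection or design feature changes.

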### **8.3.6 Patient's Global Assessment of Disease Activity (PGADA) for arthritis visual analog scale (VAS)**

The PGADA for arthritis VAS will be used to provide an overall evaluation of arthritis disease symptoms. Subjects will respond to the question, "Considering all the ways your arthritis affects you, please mark a vertical line on the scale below to show how you are feeling today," using a VAS where 0 is "very good, no symptoms" and 100 is "very poor, severe symptoms."

All subjects will complete the PGADA at Baseline. Subjects with PsA at Baseline (defined as a past medical history of PsA or PASE  $\geq 47$ ) will complete the PGADA at the visits specified in the protocol. Change from Baseline in PGADA is defined as Post-Baseline PGADA minus Baseline PGADA.

The absolute and change from baseline in PGADA will be summarized for the double-blind treatment visits separately for the RS and MS and OLS by treatment sequence and visit.

### **8.3.7 Patient Global Assessment of PSO**

The Patient Global Assessment of PSO is a PSO-specific item in which the subject responds to the multiple-choice question, "How severe are your psoriasis-related symptoms right now?" Possible responses to the question are "no symptoms," "mild symptoms," "moderate symptoms," "severe symptoms," or "very severe symptoms."

The Patient Global Assessment of psoriasis will be summarized based on OC as the primary analysis. No imputation is applied.

Shift from Baseline in Patient Global Assessment (PGA) of PSO score is defined to each Post-Baseline visit time point relative to Baseline.

The absolute value and shift from baseline in Patient Global Assessment (PGA) of PSO score will be summarized for each study period (Initial randomized, Maintenance) by treatment group.

### 8.3.8 Symptoms of PSO (Itch, pain, and scaling)

UCB has developed a new Patient Reported Outcome measure, in the form of a patient symptom diary (PSD), which is used to assess key signs, symptoms, and impacts relevant to subjects with moderate to severe chronic plaque PSO. In this study itch, pain, and scaling items from the diary will be used to assess the patient-reported level of these symptoms over time. The items will be administered on an electronic site tablet, during visits, as specified in the protocol.

Each of the 3 items is measuring the severity of the symptom. Each item will be scored separately on a 0-10 scale with 0 meaning no symptom and 10 for very severe or worst symptom.

- Change from Baseline in PSD item score for each item is defined as post Baseline PSD item score minus Baseline PSD item score.
- Percent change from Baseline in PSD item score for each item is defined as

$$\text{Percent change from Baseline} = 100 \times \frac{\text{Post Baseline PSD score} - \text{Baseline PSD score}}{\text{Baseline PSD score}}$$

Absolute and percent changes from Baseline PSD item scores for each item will be summarized for each study period (Initial randomized, Maintenance) by treatment group.

PSD response and the proportion of subjects with score of 0 (or 0/1) will be summarized for OLE Treatment Period by treatment sequence and visit.

In addition, each of the 3 PSD scores will be characterized in terms of the percent of subjects demonstrating a 4-point improvement at each visit. Subjects with a missing score will be imputed using NRI. The analysis will be limited to subjects with a Baseline PSD score at or above the applicable threshold score.

The PS0009 and PS0013 analyses determined a 4-point reduction as a marked within-subject clinically meaningful improvement in the weekly score each of these 3 PSD items that can be used to define different marked response to treatment over 16 weeks in patients with moderate-to-severe plaque psoriasis. Such a threshold has also been used to support US label claims of other compounds approved in the same indication based on different PSO symptom diaries using an 11-point numeric response scale and was suggested in previous interactions with the FDA. Analyses conducted on blinded PS0015 data support the 4-point threshold as indicative of marked within-subject clinically meaningful improvement that can be used for responder definition.

Cumulative distribution plots will also be provided for absolute change from Baseline PSD at Week 16 and Week 48 for each item.

Listings of responses to individual questions of the patient diary will be provided separately for the Initial, Maintenance, OLE, and the OLE2 treatment periods.

Summaries of PSD response (Itch, Pain, and Scaling symptoms) will be produced for the OLE2 by treatment sequence as described in Section 3.6.

